## TABLE OF AMENDMENTS:

The following amendments and/or administrative changes have been made to this protocol since the implementation of the first approved version

Amendment number	Date of amendment	Protocol version number	Type of amendment	Summary of amendment

## **STUDY SUMMARY**

Study Title:	ATNEC - Axillary management in T1-3N1M0 breast cancer patients with needle biopsy proven nodal metastases at		
	presentation after neoadjuvant chemotherapy.		
Sponsor Study Reference:	DHRD/2017/130		
Study Design:	A multi-centre phase III randomised controlled trial with embedded economic evaluation in which participants will be randomised in a 1:1 ratio.		
Study Participants:	T1-3N1M0 breast cancer patients aged 18 years or older, with needle biopsy proven nodal metastases, who after neoadjuvant chemotherapy (NACT) have no residual cancer in the lymph nodes on dual tracer sentinel node biopsy and removal of at least 3 lymph nodes (sentinel nodes and marked involved node).		
Planner Number of Sites:	~100		
Planned Sample Size:	1900 (950 per arm)		
Stratification	
 
Institution
 
Type of breast surgery (breast conserving surgery (BCS) vs mastectomy)
 
Receptor status (triple negative vs HER2 positive vs ER status positive and/or PR status positive and HER2 negative)
 
		
Intervention:	Participants in the experimental arm will not receive further axillary treatment (axillary lymph node dissection [ALND] or axillary radiotherapy [ART]), after NACT and surgery.		
Comparison/Control:	Participants in the control group will receive further axillary treatment (ALND or ART) after NACT and surgery, as per local guidelines.		
Follow Up Duration:	At least 5 years		
Planned Recruitment Start Date:	01 March 2021		
Planned Recruitment End Date:	01 March 2026		
Planned Study End Date:	28 February 2030		
Research Question/ Aims:	To assess whether, omitting further axillary treatment (ALND and ART) for patients with early stage breast cancer and axillary nodal metastases on needle biopsy, who after NACT have no residual cancer in the lymph nodes on sentinel node biopsy, is non-inferior to axillary treatment in terms of disease free survival (DFS), and reduces the risk of lymphoedema at 5 years.		

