#### 3.2. Outcome

#### 3.2.1. Co-primary outcomes:

- Disease-Free Survival (DFS); defined and calculated as the time from randomisation until the date of first event of either a loco-regional invasive breast cancer relapse, distant relapse, ipsilateral or contralateral new invasive primary breast cancer or death by any cause or the censor date.
- Lymphoedema is self-reported based on two items from the validated Lymphoedema and Breast Cancer Questionnaire (LBCQ) (arm "swelling now" and arm "heaviness in the past year"). These items have been shown to be predictive of arm swelling of a 2 cm or more change in arm circumference, but provide a simpler patient-friendly measure which has been used in other studies [17-19]. Lymphoedema will be defined as 'yes' to both questions at five years.

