#### 6.5.2. Randomised participants

Primary and secondary outcome data will be collected at randomisation and then annually for at least five years (see Appendix 2- Schedule of Assessments). We are using validated questionnaires for participant reported outcomes that have been used previously. Participant demographics, medical history, tumour characteristics and details of nodal and breast surgery will be collected at randomisation. Details of any adjuvant treatment given will also be collected during follow-up.

The required follow up data will be collected by the research nurse during routine hospital visits for annual mammogram, via hospital records or through telephone follow-up calls with participants. This data will be entered into the online study database. This will ensure high compliance with follow-up, whilst minimising the burden to participants, NHS and funder. Sites are required to report participant follow-up data annually, until all participants have reached at least five years follow-up.

Participant questionnaires with questions on arm morbidity and function, health-related quality of life and health resource use will be completed either in the clinic at randomisation. Follow-up questionnaires will be posted to participants by WCTU and returned directly to WCTU. Non-responders to postal questionnaires will receive up to two reminders by post and will then be contacted by telephone for collection of core outcomes (LBCQ and EQ-5D-5L).

Participants will be consented for collection of long-term follow-up data from existing databases via data linkage, using services such as NHS Digital, Public Health England, eDRIS (Public Health Scotland) and cancer registries; this will enable us to continue to follow-up participants and report long-term recurrence and survival.

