#### **10.1. Sample Size Calculation**

Five-year disease free survival (DFS) for participants with node negative disease after NACT was around 80% based on the pooled analysis published by von MG et al [6]. With advanced drug treatment

and improved outcome over time we would anticipate higher rates of DFS to be seen today and thus the DFS in the control arm was estimated to be 90%. Thus, assuming five years recruitment and minimum of 4.5 years follow-up, recruiting 950 participants in each trial arm (1900 in total) would have the ability to demonstrate non-inferiority of omitting further axillary treatment, defining non-inferiority as 'no worse than 3.5%' below the control arm 5-year DFS with a 5% 1-sided significance level and 85% power, allowing for 7% non-collection of primary outcome data using the POWER procedure within the SAS statistical software.

Lymphoedema is a potential side effect of further axillary treatment and hence is considered as a coprimary endpoint. The AMAROS trial reported five year lymphoedema rates for ALND of 23% (76/328) and 11% (31/286) for ART [24] based on clinical signs of lymphoedema. A meta-analysis reported a lymphoedema rate for sentinel-node biopsy of 6% [3]. A minimum 5% important difference in the proportion of participants with lymphoedema is acceptable as defined by discussions with the clinicians, the PPI group and patient co-investigators. Any differences larger than this would provide stronger evidence and have a bigger impact on clinical practice. Thus assuming similar lymphoedema rates within this trial and the majority of participants randomised to standard axillary treatment had ART (rather than ALND) then a trial of 1900 participants would have 90% power to detect at least a 5% difference between trial arms if the overall lymphoedema rate in the control arm was 11%, with a 2sided significance level and allowing for 25% dropout. The allowance for attrition is greater as the outcome is participant-reported from questionnaires. The power would be higher to detect the larger differences between trial arms that would be expected with increasing use of ALND in the standard axillary treatment arm (see Table 1).

Table 1: Sample sizes for the proportion of participants self-reporting lymphoedema symptoms at 5 years using a 5% two-sided significance level and 90% power

Proportion in	Proportion in	Difference	Sample size	Total sample	Allowing for
control arm	no axillary		in each arm	size	25% dropout

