## 10.6. Interim Analysis and Criteria for the Premature Termination of the Study

A formal interim analysis is planned when 33% of the required primary outcome events have been reported, which is anticipated to occur prior to recruitment closure. An overall 5% one-sided Type I error rate for testing non-inferiority will be controlled using an O'Brien-Fleming-like alpha-spending rule set at p = (0.01, 0.046) for the interim and final analysis respectively.

With a 5 year recruitment period, a minimum follow-up of 4.5 years, a 5 year estimated disease free survival of 90% in the control arm and 85% power, it is estimated that 282 DFS events are required for the final analysis; thus the formal interim analysis is planned when 93 DFS events have been reported. At this formal interim analysis, the trial may be stopped on the grounds of futility (i.e. conclude that it is not reasonably possible to show non-inferiority) if the obtained hazard ratio from the interim analysis is above the hazard ratio limit of 1.62 using a one-sided p-value of 0.01.

The Sponsor may suspend or prematurely terminate either the entire study, or the study at an individual site, for significant reasons that must be documented (e.g. an unacceptable risk to participants or serious repeated deviations from the protocol/ regulations). If this occurs the Sponsor shall justify its decision in writing and will promptly inform any relevant parties (i.e. participants, investigators, participating sites, REC, regulatory bodies).

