## **13. DISSEMINATION POLICY**

The dissemination of the study results will be via a study report and research papers for publication in peer reviewed journals, and presentation at relevant conferences. Reporting will be in compliance with CONSORT recommendations. Publication of the results will be based on outcomes at least 5 years following the last recruited participant. No interim publication of results is planned, any unscheduled interim publication would require approval of the TSC.

A summary of the results will be made available to participants through a newsletter (unless they state they do not wish to receive this) and will also be publicised through Independent Cancer Patients' Voice, Cancer Research UK and Breast Cancer Now.

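### The planned study end date is only 4.0 years after planned recruitment end, so it conflicts with the 5-year follow-up, the month-60 lymphoedema co-primary and the 4.5-year DFS planning assumption.

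*Protocol*

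**What the plan says.** Study Summary: recruitment is planned from 01 March 2021 to 01 March 2026, the planned study end is "28 February 2030", and the follow-up duration is "At least 5 years".

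Other sections of the protocol set the follow-up as follows:

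- Section 3.2.1: the lymphoedema co-primary requires a yes "to both questions at five years". Appendix 2 schedules the questionnaire booklet at month 60 and annual follow-up to month 120.
- Section 6.5.2: "Sites are required to report participant follow-up data annually, until all participants have reached at least five years follow-up".
- Section 6.8: the study ends at the last data capture for the last participant, with three months allowed for form return and queries.
- Section 10.1: the DFS sample size is derived "assuming five years recruitment and minimum of 4.5 years follow-up". Section 10.6 uses the same inputs for the 282-event target: "With a 5 year recruitment period, a minimum follow-up of 4.5 years".
- Section 13: "Publication of the results will be based on outcomes at least 5 years following the last recruited participant".

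**The concern.** One trial carries three minimum follow-ups: 4.0 years from the dates, 4.5 years in the DFS calculation and 5 years everywhere else. The shortest comes from the date that sites, the ethics committee and the funder would plan against.

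Lymphoedema is the outcome most exposed. It is a single response at a fixed time, so a participant who has not reached month 60 contributes nothing to it, and the response cannot be collected afterwards. Such a loss would be administrative, additional to the 25% dropout allowance in section 10.1, and concentrated in the last year of recruitment. Section 10.3.3 makes success depend on both co-primary outcomes, so a shortfall on one lowers the chance that the trial succeeds at all. DFS is less exposed, because every participant contributes follow-up time and the final analysis has an event target.

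**Working it through.** **Dates.** From 01 March 2026 to 28 February 2030 is 1460 days, or 1460/365.25 = 3.997 years. Recruitment spans 1826 days. Participants randomised after 28 February 2025 have less than 5 years by the planned end. That is the last 366 days of recruitment. Under uniform accrual (an assumption, since the protocol gives no accrual curve) the share is 366/1826 = 20.0%, and 0.200 × 1900 ≈ 381 participants.

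**Lymphoedema: reproducing the plan.** Inputs from section 10.1 and Table 1 are 11% against 6%, 5% two-sided and 90% power. With p̄ = 0.085:

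n = [1.960·√(2·0.085·0.915) + 1.282·√(0.11·0.89 + 0.06·0.94)]² / 0.05² ≈ 652 per arm.

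The continuity correction, n/4·[1 + √(1 + 4/(n·0.05))]², raises this to 691, as stated. With 1900 randomised and 25% dropout, 950 × 0.75 ≈ 712 per arm are evaluable. Power is then 92% uncorrected and 91% corrected, so the plan holds if everyone can reach month 60.

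**Lymphoedema: if the 2030 date were applied.** The same 25% dropout is applied to those who can reach month 60:

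| Share without month 60 | Evaluable per arm | Power, uncorrected | Power, corrected |
|---|---|---|---|
| 0% | 712 | 92% | 91% |
| 10% (cut-off giving 4.5 years) | 641 | 90% | 88% |
| 20% (planned date, uniform accrual) | 950 × 0.80 × 0.75 = 570 | 86% | 83% |
| 26% (planned date, 500 of 1900 in the last year) | 950 × 0.74 × 0.75 ≈ 527 | 83% | 80% |

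The last row takes the full rate in section 10.2, about 100 centres × 5 per year = 500, as reached only in the final year.

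**DFS: reproducing the plan.** Section 10.1 gives 90% control DFS and a 3.5-point margin, so the margin hazard ratio is ln 0.865 / ln 0.90 = 1.376. The Schoenfeld formula, 5% one-sided with 85% power, gives 4·(1.645 + 1.036)² / (ln 1.376)² ≈ 282 events, as stated. For the sample size, take exponential survival, uniform accrual over 5 years (R) and minimum follow-up F. The event probability is

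1 − [exp(−λF) − exp(−λ(F+R))] / (λR), with λ = 0.02107 at 90% and 0.02901 at 86.5%.

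At F = 4.5 the average over the two rates is 0.160. Then 282/0.160 ≈ 1764, and 1764/0.93 ≈ 1896, close to the stated 1900. So 282 events and 1900 participants go with 4.5 years and event rates averaged over the two arms.

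**DFS: effect of the date on that same basis.** N = 1767 is 1900 less 7%.

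| Minimum follow-up | Event probability | Events (N = 1767) | Power |
|---|---|---|---|
| 4.0 years | 0.149 | 264 | 82.9% |
| 4.5 years | 0.160 | 283 | 85.1% |
| 5.0 years | 0.170 | 301 | 87.0% |

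The lost half-year costs about 19 events and about 2 power points. With all 1900 contributing, 4.0 years still gives 284 events and 85.2% power.

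**The case against.** The strongest reply is that the 2030 date is a planned entry in a summary table, and nothing ties follow-up, database lock or analysis to it. The operative text points the other way: sites report "until all participants have reached at least five years follow-up", section 6.8 ends the study at the last participant's last data capture, section 13 bases publication on at least five years after the last recruit, and Appendix 2 schedules month 60 for all. This stands. A reader might infer from the dates that the last year of recruits can never supply the lymphoedema co-primary, or that both stated powers are missed. The documents do not support that reading, because the trial as described elsewhere would run past the date. The lymphoedema losses are therefore conditional on the date being applied, and their size depends on an assumed accrual pattern. The funding end date is not given, so an actual truncation cannot be shown.

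A reader might also compute a much larger DFS shortfall. With both arms at 90%, a 4.0-year minimum gives 225 events (N = 1767) or 242 (N = 1900), and 77-80% power. Most of that gap comes from the equal-arms event rate, not from the date: on the same basis 4.5 years gives only 242 events and 79.9% power at N = 1767. It is not the basis that reproduces the protocol's figures.

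Finally, the 4.5-year figure need not be an error. As a planning input for a time-to-event outcome it is conservative if five years are delivered. This too stands.

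The reply does not remove the contradiction. The date conflicts with the follow-up duration in its own table, and the protocol gives no rule for which prevails.

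**Conclusion.** The concern holds as an internal contradiction with a conditional consequence. The planned study end is a year short of the follow-up required elsewhere and half a year short of the DFS planning assumption.

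The lymphoedema shortfall is material if the date governs resources or data collection. It rests on uniform accrual and on 25% dropout among those who can reach month 60, and it worsens if recruitment is weighted to the last year. Even a cut-off that honours the 4.5-year minimum would leave lymphoedema below the 691 per arm in Table 1. The DFS consequence is minor on the protocol's own basis, and it disappears if the final analysis waits for the 282 events that section 10.6 requires.

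**What to change.** - Study Summary: move the planned study end to no earlier than the last participant's month-60 assessment plus the three months in section 6.8. With recruitment closing on 01 March 2026, that is 01 March 2031 plus three months, about June 2031.
- Confirm that funding and site agreements run to the corrected date.
- Section 10.3.3: state that the lymphoedema analysis waits until all participants have passed month 60.
- Sections 10.1 and 10.6: the 4.5-year minimum may stay if it is labelled a conservative DFS planning assumption and reconciled with the 5-year follow-up. Replacing it is unnecessary and would mean redoing the event projection and the stated power.

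The text changes are small, because five-year follow-up is already required elsewhere. Any real cost lies in the extension of about 15 months if budgets were set to the 2030 date, which the documents do not show.

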## FUNDING AND SUPPORT IN KIND

Funder(s)	Financial and Non-Financial Support Given
Health Technology Assessment (HTA), National Institute for Health Research (NIHR) (HTA NIHR128311)	Financial

## **ROLES & RESPONSIBILITIES**

#### Sponsor

The Sponsor, University Hospitals of Derby & Burton NHS Foundation Trust, take on overall responsibility for appropriate arrangements being in place to set up, run and report the research project. The sponsor is not providing funds for this study but has taken on responsibility for ensuring finances are in place to support the research.

#### Funder

This study is funded by the National Institute for Health Research (NIHR) Health Technology Assessment (HTA) programme (Reference - HTA NIHR128311). The views expressed are those of the author(s) and not necessarily those of the NIHR or the Department of Health and Social Care.

#### Study Management Committees

#### Trial Management Group (TMG)

The TMG will meet regularly to oversee the day-to-day management of the trial, including all aspects of the conduct of the trial. Any problems with study conduct and participating centres will be raised and addressed during TMG meetings.

The TMG will review recruitment, retention, compliance and data quality to ensure efficient trial conduct according to the research timeline. They will report to the independent Trial Steering Committee (TSC).

#### Trial Steering Committee (TSC)

The TSC will oversee and supervise the progress of the trial and ensure that it is being conducted according to the protocol and the applicable regulations. The TSC is an independent body that includes a majority of members who are not involved with the running of the trial. They will meet prior to commencement of the study, and then at regular intervals until completion (at least annually).

The TSC will take responsibility throughout the trial for:

- Proposals for substantial protocol amendments and provision of advice to the funder regarding approvals of such amendments
- Monitoring and supervising the progress of the trial
- Reviewing relevant information from other sources
- Considering recommendations from the Independent Data Monitoring and Ethics Committee
- Informing and advising on all aspects of the trial

#### Data Monitoring and Ethics Committee (DMEC)

A separate and independent DMEC will be convened. It is anticipated that the members will meet once prior to commencement of the study to agree terms of reference and on at least three further occasions to monitor accumulating data and oversee safety issues.

The DMEC will review the accruing study data and will assess whether there are any safety issues that should be brought to the participant's attention or any reasons to terminate the study. They will also review the scientific validity and the conduct of the study.

#### **Protocol Contributors**

A number of protocol contributors have been involved in the development of this protocol, these include; Chief Investigator, Co-Investigators (including patient and public representatives) and the Trial Management team. Protocol contributors are responsible for inputting into the design of the study, ensuring that it is designed transparently and efficiently.

## ATNEC

## LIST OF ABBREVIATIONS

	Adverse Event
AE ALND	Adverse Event
	Axillary Lymph Node Dissection
ANS	Axillary Node Sampling
ART	Axillary Radiotherapy
AUS	Axillary Ultrasonography
BCS Cl	Breast-conserving surgery
	Chief Investigator
CONSORT	Consolidated Standards of Reporting Trials
COSD	Cancer Outcomes and Services Dataset
CRF	Case Report Form
CT	Computerised Tomography
CTRad	Clinical and Translational Radiotherapy Research Working Group
CTU	Clinical Trials Unit
DASH	Disabilities of the Arm, Shoulder and Hand
DMEC	Data Monitoring and Ethics Committee
DN4	Doleur Neuropathique
EDC	Electronic Data Capture
ER	Estrogen receptor
FNA	Fine Needle Aspiration
FNR GCP	False Negative Rate Good Clinical Practice
HEAP	Health Economic Analysis Plan
HER2	Human epidermal growth factor receptor 2
H&E	Haematoxylin and Eosin
ICF	Informed Consent Form
ICH	International Conference on Harmonisation of technical requirements for
	registration of pharmaceuticals for human use.
ICPV	Independent Cancer Patient's Voice
ICJME	International Committee of Medical Journal Editors
IRAS	Integrated Research Application System
ISF	Investigator Site File
ITC	Isolated Tumour Cells
ISRCTN	International Standard Randomised Controlled Trials
LBCQ	Lymphoedema and Breast Cancer Questionnaire
NACT	Neoadjuvant Chemotherapy
NCRI	National Cancer Research Institute
NICE	National Institute for Health Care Excellence
NHS R&D	National Health Service Research & Development
pCR	Pathological Complete Response
Pl	Principal Investigator
PIC	Participant Identification Centre
PIL	Patient Information Leaflet
PIS	Participant Information Sheet
PPI	Patient Public Involvement
PSA	Probabilistic Sensitivity Analysis
QA	Quality Assurance
QALY	Quality-adjusted Life Year
QC	Quality Control
QoL	Quality of Life
RCT	Randomised Control Trial

## **Protocol**

REC	Research Ethics Committee
SAE	Serious Adverse Event
SAP	Statistical Analysis Plan
SDV	Source Data Verification
SOP	Standard Operating Procedure
SN	Sentinel Node
SNB	Sentinel Lymph Node Biopsy
SSDL	Site Signature and Delegation Log
TMG	Trial Management Group
TMF	Trial Master File
TNO	Trial Number
TSC	Trial Steering Committee
UHDB	University Hospitals of Derby and Burton NHS Foundation Trust
WCTU	Warwick Clinical Trials Unit

## **STUDY FLOW CHART**

\*as per local standard of care; ITCs, isolated tumour cells

## 1. BACKGROUND

There are around 55,000 new cases of breast cancer diagnosed each year. Axillary ultrasound, with needle biopsy of suspicious lymph nodes, is used in the initial diagnostic work-up of breast cancer patients. Patients with needle biopsy proven positive nodes are increasingly referred for neoadjuvant chemotherapy (NACT) to shrink the cancer before surgery. Currently after chemotherapy, all patients then undergo breast surgery (lumpectomy to remove the cancerous lump or mastectomy to remove the breast) and treatment to their axilla, either removal of all lymph nodes in the axilla (axillary lymph node dissection (ALND)) or radiotherapy to axilla (ART). National Institute for Health and Care Excellence (NICE) recommends ALND to patients who have a preoperative ultrasound-guided needle biopsy with pathologically proven lymph node metastases [1].

After ALND a drain is left in the wound to drain excess fluid or blood for a few days afterwards. The operation lasts one to two hours and may require an overnight stay in the hospital. This procedure delays the return to usual activities and paid work [2].

Axillary radiotherapy (ART) is radiation targeted at the axilla and is used instead of ALND in some hospitals based on local guidelines. The radiation is given five days a week for three to five weeks. Axillary radiotherapy is offered only in some specialist centres, and so patients may need to travel a considerable distance for treatment.

ALND or ART damages lymphatic drainage from the arm and both are associated with increased risk of lymphoedema, restricted shoulder movement or shoulder discomfort, pain, sensory changes and numbness[2]. These adverse effects interfere with daily activities, impair health-related quality of life (QoL) and are costly to the NHS in terms of rehabilitative treatments as they can be chronic and often irreversible with limited symptom relief.

The findings of a systematic review suggest that more than one in five women who survive breast cancer will develop arm lymphoedema [3]. Lymphoedema has a negative psychosocial impact on affected individuals resulting in negative self-identity, emotional disturbance, psychological distress, marginalization, perceived diminished sexuality and social isolation [4].

The cost of axillary treatment in the UK NHS is around £2600 per patient (National HRG tariff). Additional costs come from demand on the lymphoedema clinics, physiotherapy, follow-up clinics and pressures on primary care (e.g. district nurses for drain removal after ALND). These are estimated to be around £500 per patient and a simple cost analysis suggests an average overall cost saving of £3100 per patient from having no further axillary treatment.

The improvement in the life expectancy of patients with breast cancer raises important questions about how to improve the QoL for those sustaining complications of breast cancer treatment. The risks and benefits of axillary treatment should be carefully considered by clinicians and patients.

NACT results in eradication of cancer in the axillary lymph nodes in 40% to 70% of patients [5, 6]. This has raised questions about the benefit of further axillary treatment in these patients with no evidence of residual disease in the lymph nodes. A meta-analysis[7] and two prospective multicentre studies (Z1071 and SENTINA) [8, 9] showed that the presence or absence of residual disease in the lymph nodes after chemotherapy can be accurately and reliably determined by dual tracer sentinel lymph node biopsy (SNB) and by removing at least three axillary lymph nodes. All patients in the two studies underwent ALND following SNB. The Z1071 trial [8] showed that the sentinel node was successfully identified and removed in 92.5% patients and the false-negative rate (FNR) was 12.6%. The SENTINA trial [9] reported 80% success rate of SNB and 14% FNR. The FNR decreased when dual mapping agents were used and was less than 10% when ≥3 nodes were removed. Additionally, marking the abnormal

axillary lymph nodes at the time of needle biopsy with either a clip or by tattooing to allow for localisation and removal of the known metastatic node following NACT further reduces the FNR [10, 11]. In around 80% of cases, the marked node is the sentinel node when at least three nodes are removed [12]. A meta-analysis showed that the combination of SNB with removal of the marked node reduces the FNR to less than 5% [13].

SNB is minimally invasive and associated with lower risk of arm morbidity and improved patient QoL outcomes compared with ALND or ART [2]. However, we need to ensure that de-escalation of axillary treatment to limit treatment-related morbidity does not compromise the risk of cancer recurrence and survival. This study will determine whether, omitting further axillary treatment (ALND and ART) for patients with early stage breast cancer and axillary nodal metastases on needle biopsy, who after NACT have no residual cancer in the lymph nodes on SNB, is non-inferior to axillary treatment on outcomes of cancer recurrence, lowers the risk of arm lymphoedema at five years, and whether it represents a worthwhile use of NHS resources.

